5.6.4.2 Presentations

For all continuous laboratory assessments the absolute values and change in each parameter from baseline to each post-baseline visit will be summarised using descriptive statistics at each time point by dose level/cohort as appropriate. Graphical presentations using box plots

of absolute values and change from baseline values for haematology and clinical chemistry parameters will also be shown.

Laboratory abnormalities occurring from the start of IP administration to the last assessment on study will be presented. Worst toxicity grade, rates of grade 3-4 toxicity, and grade shifts of 2 or more from baseline to the maximum grade will be presented.

Summaries indicating hyper- and hypo- directionality of change will be produced, where appropriate. Laboratory parameters that cannot be graded via NCI Common Terminology Criteria for Adverse Events (CTCAE) will be summarised with frequencies of post-baseline laboratory values categorized as low (L), normal (N), or high (H) using laboratory normal ranges compared to baseline.

Listings will be provided for all laboratory results. Laboratory parameters will be assessed at baseline as well as throughout the study.

Also, a separate table for the changes in platelets and neutrophils will be summarised over time per dose level/cohort, as appropriate.

Liver Function Parameters

Number and percentage of participants with elevated post-baseline ALT, AST, or Total Bilirubin will be tabulated. Individual patient data where elevated ALT or AST plus total bilirubin fall into the “Potential Hy’s law” will be summarised and/or listed.

Following Safety Review Committee (SRC) review of emerging data additional laboratory safety assessment sample times may be added or removed if indicated by the emerging data. For presentation of the results this analysis plan will follow the initial time schedule for these parameters.

5.6.5 Clinical Laboratory, Urinalysis

5.6.5.1 Definitions and Derivations

Laboratory urinalysis variables that will be measured are detailed in [Table 3](#). Laboratory parameters will be assessed at baseline as well as throughout the study.

Change from baseline in urinalysis endpoints will be calculated for each post-dose visit. CTC grade will be calculated at each visit for tests with CTC grading defined. Maximum post-baseline CTC will also be calculated. Absolute values will be compared to the local laboratory reference and classified as low (below range), normal (within range or on limits of range) and high (above range). All values classified as high or low will be flagged on the listings.

5.6.5.2 Presentations

Laboratory abnormalities occurring from the start of IP administration to the last assessment on study will be presented. Worst toxicity grade, rates of grade 3-4 toxicity, and grade shifts of 2 or more from baseline to the maximum grade will be presented. Summaries indicating hyper- and hypo- directionality of change will be produced, where appropriate. Laboratory parameters that cannot be graded via NCI CTCAE will be summarised with frequencies of post-baseline laboratory values categorized as low (L), normal (N), or high (H) using laboratory normal ranges compared to baseline.

Listings will be provided for all laboratory results including urinalysis.

5.6.6 Vital Signs

5.6.6.1 Definitions and Derivations

Body temperature, blood pressure, pulse rate, oxygen saturation and body weight will be assessed.

5.6.6.2 Presentations

Vital signs will be assessed at baseline and throughout the study. Vital signs may be summarised by study visit which may include descriptive statistics for the value of the parameters and the changes from baseline.

Absolute values and change from baseline for vital signs data at each timepoint will be presented using box plots.

5.6.7 B symptoms

5.6.7.1 Presentations

Information on B symptoms (unintentional weight loss of 10% or more within the previous 6 months, Disease related intermittent fevers >38 C for ≥ 2 weeks without other evidence of infection, Drenching Sweats Especially at Night for > 1 month without evidence of infection, Worsening of B-symptoms compared to baseline, Worsening of B-symptoms compared to prior visit, commnets) will be listed for all patients and visits.

5.6.8 Tumour lysis syndrome

5.6.8.1 Definitions and Derivations

Tumour lysis syndrome (TLS) is an important identified risk for AZD0466. TLS prophylaxis is mandatory for all patients starting 3 days before the first dose of AZD0466, which should be followed in addition to institutional guidelines.

5.6.8.2 Presentations

Listing of TLS Monitoring including potassium, calcium, phosphate, uric acid, cardiac arrhythmia, seizure, grade and creatinine abnormality will be presented.

A TLS-key patient table should be provided. The listing should include: Highest CTCAE grade for TLS event, presence of laboratory TLS (present/non-present), highest Cairo Bishop ([Cairo and Bishop 2004](#)) grading for clinical TLS event (if criteria clinical TLS are met).

5.6.9 Electrocardiogram

5.6.9.1 Definitions and Derivations

Electrocardiogram (ECG) parameters (triplicate recordings) will be assessed at baseline as well as throughout the study. The average of the triplicate measures taken will be used in all calculations. ECG parameters include PR, RR, QRS, QT, QTcB, and QTcF. The QTcF is considered as the primary correction method to assess patient cardiac safety.

From these resting 12-lead ECGs values of the QT and RR intervals and the QT interval corrected for heart rate using Fridericia's correction (QTcF) will be derived using the following formula:

$$\text{QTcF} = \frac{\text{QT}}{\sqrt[3]{\text{RR}}} \text{ where RR is in seconds}$$

The values of QTcF (milliseconds) will be re-derived from the values of RR and QT during the creation of the reporting database.

The notable ECG interval values while on treatment are:

- Maximum QTcF, QTcB and QTc intervals > 450 milliseconds, > 480 milliseconds, and > 500 milliseconds.
- Maximum changes from baseline in QTcF and QTcB > 30, >60, and > 90 milliseconds.

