6.6.6.5 Cardiac Findings

AZD0466 should be withheld if any of the following occur at any time during study intervention:

- Symptomatic tachycardia
- Symptomatic hypotension
- QTcF shortening by 60 milliseconds compared to baseline, or interval value < 340 milliseconds, confirmed on at least 2 separate ECGs recorded 5 minutes apart
- QTcF prolongation of > 500 milliseconds or QTcF prolongation from baseline by 60 milliseconds, confirmed on at least 2 separate ECGs recorded 5 minutes apart
- Any other cardiac findings of CTCAE Grade ≥ 2 or considered by the Investigator to be clinically significant.
- AZD0466 should be permanently discontinued if a CTCAE Grade ≥ 3 cardiac AE of any duration occurs during study intervention, if considered by the Investigator to be related to study intervention.

Further investigation of the cardiac findings should be considered, including referral to a cardiac specialist. Patients should be monitored closely. AZD0466 may be restarted after resolution of cardiac findings to the patient's baseline at the discretion of the Investigator and after discussion with the Study Physician.

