4.3.3 General Study Level Definitions

Baseline is the last non-missing value obtained prior to the first dose/administration of any study treatment and any information collected after first dose/administration of study treatment is regarded as post-baseline information. If two visits are equally eligible to assess patient status at baseline (e.g., screening and baseline assessments both on the same date prior to first dose/administration with no washout or other treatment in the screening period), the average is taken as the baseline value. For non-numeric laboratory tests (i.e. some of the urinalysis parameters) where taking an average is not possible then the best value is taken as baseline as this is the most conservative. In the scenario where there are two assessments on Day 1 prior to first dose, one with time recorded and the other without time recorded, the one with time recorded is selected as baseline. Where safety data are summarised over time, study day is calculated in relation to date of first treatment. For assessments on the day of first dose where time is not captured, a nominal pre-dose indicator, if available, serves as sufficient evidence that the assessment occurred prior to first dose. Assessments on the day of the first dose where neither time nor a nominal pre-dose indicator are captured is considered prior to the first dose if such procedures are required by the protocol to be conducted before the first dose. If no value exists before the first dose/administration, then the baseline value is treated as missing.

Change from baseline will be calculated as the post-dose value minus the baseline value as:

$$\text{post-baseline value} - \text{baseline value}$$

Percent change from baseline will be calculated as:

$$\frac{\text{post-baseline value} - \text{baseline value}}{\text{baseline value}} \times 100$$

Study day 1 is defined as the date of first dose of study treatment (Cycle 1 Day 1). For visits (or events) prior to first dose, study day is defined as (date of visit [event] – date of first dose of study treatment). For visits (or events) that occur on or after first dose of study treatment, study day is defined as (date of visit [event] – date of first dose of study treatment + 1).

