5.6.9.2 Presentations

ECG parameters will be summarised using descriptive statistics by visit and change from baseline in ECG endpoints will be calculated for each post-dose visit. Absolute values and change from baseline for ECG data at each timepoint will be presented using boxplots.

The number and percentage of patients having notable ECG interval values on treatment will be summarised.

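### The SAP's table of notable ECG values has no row for QTcF shortening, although the protocol lists shortening as a reason to withhold AZD0466

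*SAP*

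**What the plan says.** Protocol 6.6.6.5 (Cardiac Findings) opens its list with "AZD0466 should be withheld if any of the following occur at any time during study intervention". Four QTcF criteria follow, in two pairs:

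- shortening: "QTcF shortening by 60 milliseconds compared to baseline, or interval value < 340 milliseconds";
- prolongation: "QTcF prolongation of > 500 milliseconds or QTcF prolongation from baseline by 60 milliseconds".

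Each pair has to be confirmed on at least two separate ECGs recorded 5 minutes apart.

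SAP 5.6.9.1 names QTcF as the primary correction for cardiac safety and averages the triplicate readings. Its notable on-treatment values are "Maximum QTcF, QTcB and QTc intervals > 450 milliseconds, > 480 milliseconds, and > 500 milliseconds" and "Maximum changes from baseline in QTcF and QTcB > 30, >60, and > 90 milliseconds". There is no minimum and no decrease category. SAP 4.3.3 defines change as the post-baseline value minus the baseline value.

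SAP 5.6.9.2 then states: "The number and percentage of patients having notable ECG interval values on treatment will be summarised". It also plans by-visit descriptive statistics and boxplots of values and changes. Under SAP 4.3.4, by-visit tables use the value closest to the scheduled date when a window holds more than one. Summaries of extreme values use every post-baseline value, including unscheduled ones.

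**The concern.** The protocol treats a fall in QTcF as a reason to withhold drug, alongside a rise. The SAP's threshold table looks only upward. A patient can therefore have dosing held on a QTcF criterion and still be absent from the table that counts patients with notable ECG values.

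Change from baseline in electrocardiograms is a Part A primary endpoint (Protocol Section 3, Table 2; SAP 2.1, Table 1). The notable-value table is the only ECG output described in SAP 5.6.9.2 that sets patients against thresholds. Someone using it to see how many patients at a dose level crossed a QTcF limit would get an answer for prolongation and none for shortening, with nothing to show that the second question was not asked.

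**Working it through.** The plan gives no figure to reproduce. The check is whether a reading that meets each protocol criterion must fall in at least one SAP row.

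**Inputs.** Let B be baseline QTcF and V an on-treatment QTcF, both in ms.

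- Protocol 6.6.6.5: B − V ≥ 60; V < 340; V > 500; V − B ≥ 60. Reading the 60 ms limits as inclusive is an assumption, since the protocol does not say.
- SAP 5.6.9.1: V > 450, 480 or 500; V − B > 30, 60 or 90.
- Range of B: below 470, from the cardiac exclusion criterion in Protocol 5.2 (which exempts patients with a pacemaker). The lower limit of 340 is an assumption.

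**Reasoning by criterion.**

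- Shortening by 60 ms or more: V ≤ 469 − 60 = 409, below 450, and V − B ≤ −60. No row applies.
- V < 340: V is below 450, and V − B ≤ 339 − 340 = −1. No row applies.
- V > 500: falls in all three absolute rows.
- Rise of 60 ms or more: exceeds 30, so at least the > 30 row applies.

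**Enumeration.** All whole-millisecond pairs with B from 340 to 469 (130 values) and V from 280 to 560:

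| Protocol criterion | Pairs meeting it | Pairs in no SAP row |
|---|---|---|
| Shortening ≥ 60 ms | 1 + 2 + … + 130 = 130 × 131 / 2 = 8,515 | 8,515 |
| V < 340 ms | 60 × 130 = 7,800 | 7,800 |
| Rise ≥ 60 ms | 130 × (161 + 32) / 2 = 12,545 | 0 |
| V > 500 ms | 60 × 130 = 7,800 | 0 |

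These counts show which combinations the rows cover. They are not probabilities.

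**Examples.**

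- 405 to 335 ms: 335 − 405 = −70. Both shortening limits are crossed; no SAP row applies.
- 420 to 360 ms: −60. One shortening limit is met; no SAP row applies.
- 380 to 440 ms: +60. The rise limit is met; counted under > 30.
- 420 to 481 ms: +61. Counted under change > 30 and > 60, and under > 450 and > 480.

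**QTcB.** The check above uses QTcF, but the SAP applies its rows to QTcB as well. With Bazett's formula QT/√RR and the SAP's QTcF formula, QTcB/QTcF = RR^(−1/6). A shortened QTcF of 409 ms reaches QTcB > 450 ms only if RR < (409/450)^6 = 0.564 s, which is above about 106 beats per minute. For 335 ms the limit is (335/450)^6 = 0.170 s, about 352 beats per minute. A fast heart rate can thus occasionally bring such a patient into a QTcB row, but the patient is then counted as prolonged, not as shortened.

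**The case against.** The strongest reply is that a shortening is not hidden.

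- SAP 4.3.2 reports minima as well as means, so at a small dose level a QTcF of 335 ms at a summarised visit would appear as the minimum or bound it from above. Boxplots show it too.
- Protocol 9.4.3.2 lists ECG data by patient.
- SAP 5.6.1.2 summarises dose interruptions with reasons, and SAP 5.6.2.2 tabulates AEs leading to interruption.
- A medical review of ECG data for other significant AEs is planned (Protocol 9.4.3.1; SAP 5.6.2.1).

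All of this stands, and it rules out the reading that shortening goes unreported. It does not supply the missing count. By-visit tables do not count patients against a limit. The interruption tables do not identify the QTcF criterion, and the AE route needs an AE to have been recorded. An unscheduled ECG can lose its place in a by-visit table to a value closer to the scheduled date, and the one ECG summary that uses all readings has no lower limit.

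A second reply is that nothing in the SAP says the table should reproduce the number of holds. That is correct, and averaged triplicates do not apply the rule of two separate confirming ECGs in any case. Rows for shortening would approximate holds, as the prolongation rows already do.

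Third, the cardiovascular risk named in Protocol Table 1 is QRS change and myocardial oedema, and the ECG event of special interest is a decrease in QRS amplitude. Neither is QT shortening, so the case should rest on the primary endpoint and the protocol's own criteria.

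Finally, the table specifications are in a separate document and may already contain such rows. If so, the SAP text should say so.

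**Conclusion.** The point holds in a limited form. The SAP's notable categories cover prolongation only. A patient who meets a QTcF shortening criterion and has no reading in a prolongation row is not counted. This concerns two of the four QTcF criteria in Protocol 6.6.6.5.

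It rests on the signed definition of change in SAP 4.3.3, on a baseline QTcF between 340 and 469 ms, and on the absence of a fast-rate QTcB reading as described above. If maximum change were instead read as the largest absolute change, shortenings would enter the change rows but could not be told apart from rises, and a value below 340 ms with a small change would still be missed.

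Three stronger readings are tempting, and the documents do not support them:

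- *Changes count only above 60 ms, so a rise of exactly 60 ms is lost.* The SAP line also has a > 30 row, which counts that patient. What remains is a mismatch between the > 60 row and the protocol's "QTcF prolongation from baseline by 60 milliseconds", and only if the latter is inclusive.
- *All patients held for ECG reasons are missing from the table.* Both QTcF prolongation criteria are captured in every case examined.
- *The understatement can be given as a percentage of a dose level.* The current text has the dose-level sizes blacked out, and the documents give no incidence of shortening.

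This is a small, low-cost improvement to a safety count. It does not undermine the ECG analysis.

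**What to change.** In SAP 5.6.9.1 add two notable categories:

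- minimum on-treatment QTcF < 340 ms;
- maximum decrease from baseline in QTcF ≥ 60 ms.

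Derive both from all on-treatment values, including unscheduled ones, as SAP 4.3.4 already provides for extreme values, and tabulate them by dose level/cohort in SAP 5.6.9.2. Add a footnote that the rows use averaged values and do not apply the protocol's confirmation on at least two separate ECGs, so they approximate holds and do not reproduce them.

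Optionally, make the boundary of the > 60 ms row agree with the protocol's 60 ms rise, after clarifying whether exactly 60 ms is meant to be included.

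The cost is a few lines of SAP text, two table rows and a footnote, with no new data. The limits are those already in the protocol, used here for reporting only; the change takes no view on whether they are the right clinical thresholds.

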5.6.9.2 Presentations

ECG parameters will be summarised using descriptive statistics by visit and change from baseline in ECG endpoints will be calculated for each post-dose visit. Absolute values and change from baseline for ECG data at each timepoint will be presented using boxplots.

The number and percentage of patients having notable ECG interval values on treatment will be summarised.

5.6.10 Echocardiogram (ECHO)

5.6.10.1 Definitions and Derivations

In addition to screening, an ECHO should be done within 14 days after an abnormal ECG finding (T wave inversion/flattening, significant QRS amplitude changes or symptomatic patient, etc) or as soon as possible when clinically indicated. If an ECHO cannot be taken, a multi-gated acquisition (MUGA) scan to assess left ventricular ejection fraction (LVEF)

will be done. In case of any T wave abnormality, the ECHO (or MUGA) should be repeated at the 30-day follow-up visit to address the question of recovery, during the off-treatment period.

5.6.10.2 Presentations

Absolute value, change from baseline and percentage change from baseline will be presented for LVEF.

5.6.11 Other Safety Assessments

Refer to the individual modules.

6 INTERIM ANALYSIS - CORE

Refer to the individual modules.

7 STUDY OBJECTIVES – MODULE 1

The objectives and endpoints for the module 1 are provided below.

[figure not shown]
Refer to Section 2.1. Exploratory endpoints related to the pharmacodynamics, biomarkers and DNA may be reported outside of the CSR and will not be described further within this SAP.

8 STUDY DESIGN – MODULE 1

8.1 Schema

The schema for Module 1 Part A and Part B is illustrated in [Figure 1](#).

Figure 1 Module 1 Schema

^a Alternative dosing schedule: option of dose reduce and/or change in dosing schedule from weekly to every 2 weeks based on emerging safety data.

B-NHL = B-cell non-Hodgkin lymphoma; DL = dose level; DLBCL = diffuse large B-cell lymphoma; FL = follicular lymphoma; MCL = mantle cell lymphoma; MTD = maximum tolerated dose; MZL = marginal zone lymphoma; RP2D = recommended Phase II dose; R/R = relapsed/refractory.

In part A, the initial dose levels will be set according to nonclinical modelling and data from previous studies with an intra-patient dose ramp-up to mitigate the risk of TLS. The intra-patient ramp-ups will involve beginning at a specified lower dose and rapidly increase the dose to reach target value by Day 8. For example, in dose level 1, at Cycle 1 Day 1 AZD0466 will be administered at 150 mg followed by 300 mg at Cycle 1 Day 4 and reaching target dose of 600 mg at Cycle 1 Day 8. Thereafter, weekly dosing would continue at 600 mg. Each cycle is 28 days with Cycle 1 consisting of ramp-up to achieve the target dose level and then 3 doses at target level on Days 8, 15, and 22 with a 28-day DLT period (refer to Section 10.6.6.2 of the CSP for details).

8.2 Overall Design

Module 1 will evaluate the safety, tolerability, PK, and preliminary efficacy of AZD0466 as monotherapy. Module 1 comprises 2 parts: AZD0466 monotherapy dose escalation in patients with advanced B-NHL (Part A) followed by 3 independent dose expansion cohorts of patients with defined lymphoid malignancies (Part B). The Module 1 schema is illustrated in [Figure 1](#).

- **Part A:** Phase 1 dose setting to assess the safety and tolerability and determine dose(s) and schedule(s) to be evaluated in Part B.
- **Part B:** Phase 1b/2a dose expansion to assess the preliminary efficacy of AZD0466 in 3 select patient populations: Relapsed/refractory-Mantle cell lymphoma (R/R MCL) (Cohort B1) , Relapsed/refractory follicular lymphoma (R/R FL) or Relapsed/refractory Marginal zone lymphoma (RR MZL) (Cohort B2), and Relapsed/refractory diffuse large B-cell lymphoma (RR DLBCL) (Cohort B3).

An SRC will be responsible for making recommendations for dose escalation or dose de-escalation decisions after each dose level. The SRC will also assess all evaluable patients to establish the Recommended Phase II dose (RP2D) and determine if the study should progress to Part B. Refer to Appendix A 5 A5 of the CSP for details on the SRC. Further details on the decision rules for dose escalation are described with in the SRC charter.

Treatment will be administered in the outpatient setting with close monitoring. All patients will be treated until disease progression or unacceptable toxicity or withdrawal of consent. All patients should be followed for survival every 3 months after the last clinic visit until withdrawal of consent or end of study for the purpose of assessing survival status (see Section 7.1 of CSP). Patients who achieve a CR will be followed for relapse of disease until death.

9 CHANGES TO PLANNED PROTOCOL ANALYSES – MODULE 1

Not Applicable.

10 DATA ANALYSIS CONSIDERATION – MODULE 1

10.1 Timing of Analyses

The details of the analyses planned during the conduct of this study is outlined in [Table 5](#).

Table 5 Summary of analyses During Study Conduct

| Analysis | Trigger |
|--|--|
| Analysis Part A: Dose Escalation | When the MTD has been determined and the last patient to be recruited has had the opportunity to complete 2 cycles of treatment or has discontinued or withdrawn from treatment. |
| Interim Analysis Part B: cohort B1 | Interim analysis will be performed when CCI [REDACTED]. |
| Interim Analysis Part B: cohort B2 | Interim analysis will be performed when CCI [REDACTED]. |
| Final Analysis Expansion Cohorts (B1, B2 and B3) | Final analysis will be performed when either the last patient from all expansion cohorts has had the opportunity to CCI [REDACTED]. |

